7. DISCONTINUATION OF STUDY INTERVENTION AND PARTICIPANT DISCONTINUATION/WITHDRAWAL

7.1. Discontinuation of Study Intervention

A participant may withdraw from the study treatment at any time at his/her own request or may be withdrawn at any time at the discretion of the Investigator for safety, behavioural or administrative reasons. Participants that are discontinued from treatment will enter the post-treatment period unless consent is withdrawn. Every effort should be made to complete the early termination (ET) study procedures and observations if the participant does not enter post-treatment follow-up.

Any laboratory parameter that meets the stopping criteria should be repeated to confirm the value prior to withdrawal

In rare instances, it may be necessary for a participant to permanently discontinue (definitive discontinuation) study intervention. If study intervention is definitively discontinued, the participant may remain in the study to be evaluated for safety and efficacy assessments. For participants meeting the stopping criteria (Section 7.1.1-Section 7.1.4), participants should be monitored until laboratory abnormalities resolve, stabilize, or return to within baseline values as indicated. The participant must then attend the follow-up visits specified in the SoA. See the SoA for data to be collected at the time of discontinuation of study intervention and follow-up and for any further evaluations that need to be completed.

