7.1.1. Liver Chemistry Monitoring and Stopping Criteria

Liver chemistry monitoring and stopping criteria have been designed to assure participant safety and to evaluate liver event etiology. Study intervention will be discontinued for a participant if the liver stopping criteria are met. Restart/re-challenge guidelines are presented in Section 10.6.

Discontinuation of study intervention for abnormal liver tests is required when:

- a participant meets one of the discontinuation conditions outlined in Table 6
- when in the presence of abnormal liver chemistries not meeting protocol-specified stopping rules, the investigator believes study intervention discontinuation is in the best interest of the participant.

Table 6 lists the criteria for withholding or discontinuing the study medication in a study participant with elevation of ALT. Additional testing will be performed (see safety follow-up procedures for participants who meet increased monitoring or stopping criteria) and the participant monitored until liver chemistry abnormalities resolve, stabilize, or return to within baseline values. The participant must then attend the follow-up visits specified in the SoA.

Every attempt must be made to have the participant evaluated (within 24 hours) for repeat assessment of liver chemistries and additional testing and close monitoring (a specialist or hepatology consultation is recommended). Participants must be monitored twice weekly until liver chemistry abnormalities (ALT, AST, alkaline phosphatase, bilirubin)

resolve, stabilize, or return to within baseline values. Upon completion of the safety follow-up procedures (see below), the participant must attend the follow-up visits specified in the SoA.

Table 6 Liver Chemistry Monitoring and Stopping Criteria-

ALT Level	Monitoring Plan	Discontinuation
10x ULN ≤ ALT <12x ULN and Bilirubin ≤1.5x ULN and INR ≤1.5 (if available)	Monitor twice weekly Additional lab assessments	Permanently discontinue IMP if ALT >10x ULN >4 weeks

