ALT ≥12x ULN and Bilirubin≤1.5x ULN and INR ≤1.5 (if available) ALT ≥3x ULN and	Hold dose Monitor twice weekly Additional lab assessments if not already done Take off hold: 150 mg SC weekly when ALT <10x ULN; increasing dose to 300 mg (if applicable) should be agreed with Medical Monitor Hold dose Monitor twice weekly Additional lab assessments if not	Permanently discontinue IMP if any of the following apply: ■ ALT ≥10x ULN >4 weeks ■ ALT ≥12x ULN recurs after IMP taken off hold Permanently discontinue IMP if the following recurs
1.5x ULN <bilirubin (="" uln="" ≤2x="">35% direct) and INR ≤1.5 (if available)</bilirubin>	already done Take off hold: 150 mg SC weekly when bilirubin returns to <1.5x ULN; increasing dose to 300 mg (if applicable) should be agreed with Medical Monitor For participants not receiving NA therapy at baseline, initiate NA therapy¹	after IMP taken off hold: 1.5x ULN <bilirubin (="" uln="" ≤2x="">35% direct) And INR ≤1.5 (if available)</bilirubin>
ALT ≥3x ULN and any of the following apply: • bilirubin >2x ULN (>35% direct) • associated with the appearance or worsening of hepatitis symptoms • INR >1.5 (if available)		Permanently discontinue IMP Monitor twice weekly until stable ALT Additional lab assessments if not already done For participants not receiving NA therapy at

ALT Level	Monitoring Plan	Discontinuation
		baseline, initiate NA therapy¹

ALT = alanine aminotransferase; IMP = investigational medicinal product; ULN = upper limit of normal 1. NA therapy may be subsequently discontinued if other tests (e.g., HBV DNA, HBsAg) rule out hepatitis B flare.

*Notes:

- Any abnormal laboratory parameters that meet the criteria for individual treatment discontinuation must be confirmed by retest of a new collection of blood samples as soon as possible.
- Deterioration considered clinically significant from the baseline in the liver parameters must be confirmed by retesting ALT, total bilirubin, direct bilirubin, and INR (if available).
- If one criterion in the list above is met and confirmed by retesting, further treatment may be discontinued for this participant after discussion with the Medical Monitor. Results of retesting must be evaluated before the next dose is administered.
- Monitor participant until liver chemistry abnormalities resolve, stabilize, or return to within baseline values.

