10.5. Appendix 5: Genetics

USE/ANALYSIS OF DNA

- Genetic variation may impact a participant's response to study intervention, susceptibility, severity and progression of disease. Variable response to study intervention may be due to genetic determinants that impact drug absorption, distribution, metabolism, and excretion; mechanism of action of the drug; disease etiology; and/or molecular subtype of the disease being treated. Therefore, where local regulations and IRB/IEC allow, a blood sample will be collected for DNA analysis
- DNA samples will be used for research related to GSK3228836 or CHB and related diseases. They may also be used to develop tests/assays including diagnostic tests related to GSK3228836 or other 2'-MOE ASOs, and CHB. Genetic research may consist of the analysis of one or more candidate genes or the analysis of genetic markers throughout the genome or analysis of the entire genome (as appropriate)
- Additional analyses of DNA samples may be conducted if it is hypothesized that this may help further understand the clinical data.
- The samples may be analyzed as part of a multi-study assessment of genetic factors involved in the response to GSK3228836 or study interventions of this class. The results of genetic analyses may be reported in the clinical study report or in a separate study summary.
- The sponsor will store the DNA samples in a secure storage space with adequate measures to protect confidentiality.
- The samples will be retained while research on GSK3228836 (or study interventions of this class) or CHB continues but no longer than 15 years after the last participant last visit or other period as per local requirements.

10.6. Appendix 6: Liver Safety: Required Actions and Follow-up Assessments and Study Intervention Restart/Rechallenge Guidelines

Phase 2 liver chemistry stopping and increased monitoring criteria have been designed to assure participant safety and evaluate liver event etiology.

The procedures listed below are to be followed if a participant meets any of the liver chemistry stopping criteria defined in Section 7.1.1.

- Immediately withdraw the participant from study treatment.
- Notify the Medical Monitor within 24 hours of learning of the abnormality to confirm the participant's study treatment cessation and follow-up.
- Complete the Liver Event CRF.
- Complete the "Safety Follow-up Procedures" listed below.

Safety Follow-up Procedures for Participants Who Meet *Any* of The Stopping Criteria:

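### Protocol Section 7.1.1 requires treatment to stop when a Table 6 liver discontinuation condition is met, but a note under the table makes stopping optional once the criterion is confirmed.

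*Protocol*

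**What the plan says.** Section 7.1.1 of the protocol states the rule twice in mandatory terms. It opens with "Study intervention will be discontinued for a participant if the liver stopping criteria are met". It then says "Discontinuation of study intervention for abnormal liver tests is required when" a participant meets a discontinuation condition in Table 6, or when the investigator judges stopping to be best despite no stopping rule being met.

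Table 6 has four rows. The first three call for monitoring or a dose hold, with permanent discontinuation only if the abnormality persists or recurs. The last row covers ALT at least 3x ULN with any of bilirubin above 2x ULN (more than 35% direct), INR above 1.5, or new or worsening hepatitis symptoms. Its Discontinuation cell begins, with two lines run together, "Permanently discontinue IMP Monitor twice weekly until stable ALT".

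The notes under the table say that values meeting the discontinuation criteria "must be confirmed by retest of a new collection of blood samples as soon as possible". The third note reads "If one criterion in the list above is met and confirmed by retesting, further treatment may be discontinued for this participant", following discussion with the Medical Monitor. It adds that the retest result has to be evaluated before another dose. A later note sends cases such as Gilbert syndrome to the Medical Monitor, because such a participant may be able to continue.

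Two other places bear on this. Section 7.1 says "Any laboratory parameter that meets the stopping criteria should be repeated to confirm the value prior to withdrawal". Appendix 6 (Section 10.6) says "The procedures listed below are to be followed if a participant meets any of the liver chemistry stopping criteria defined in Section 7.1.1", and its first step is "Immediately withdraw the participant from study treatment".

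**The concern.** One section gives two instructions for the same event. After a confirmed discontinuation criterion, the main text and the table require stopping, while the note permits it. A liver stopping rule should tell every site the same thing, above all in the row that describes the most serious pattern. Appendix 2 (Table 13, note 3) says that ALT at least 3x ULN with bilirubin above 2x ULN or INR above 1.5 may indicate severe liver injury of the Hy's Law type, and makes such events reportable as SAEs.

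The ALT part of that row may not be rare. Section 4.2.1 reports that 33% of treatment-naïve participants in the earlier four-week study reached ALT of at least 3x ULN, without changes in bilirubin or INR. The added trigger is therefore what decides whether the row applies, and the instruction that follows should not be in doubt.

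At stake are participant safety and consistent conduct across sites. SAP Section 4.5.3.1 summarises liver monitoring and stopping events by reference to protocol Section 7.1.1, so uneven application would also make those summaries harder to read.

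**Working it through.** No formula applies, and the plan gives no figure to reproduce. The check sets the statements side by side.

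**1. Mandatory against discretionary wording in Section 7.1.1**

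- Mandatory: two statements in the running text, plus a permanent-discontinuation instruction in the Discontinuation column of each of the four rows. 2 + 4 = 6.
- Discretionary: the third Table 6 note. 1.

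The count shows which way the section intends to point. It does not measure consequence.

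**2. Where the two collide at first occurrence**

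| Table 6 row | First action | Permanent discontinuation |
|---|---|---|
| 1: ALT 10x to below 12x ULN, bilirubin and INR each no more than 1.5 (x ULN for bilirubin) | Monitor | ALT above 10x ULN for more than 4 weeks |
| 2: ALT at least 12x ULN, same bilirubin and INR limits | Hold | ALT at least 10x ULN for more than 4 weeks, or recurrence of at least 12x ULN after the hold |
| 3: ALT at least 3x ULN, bilirubin above 1.5x to 2x ULN, INR no more than 1.5 | Hold | Recurrence after the hold |
| 4: ALT at least 3x ULN with bilirubin above 2x ULN, INR above 1.5 or symptoms | Stop | Immediately applicable |

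Only 1 of 4 rows requires permanent discontinuation at first occurrence. In rows 1 to 3 a permissive note fits the first event, because the first action is only to monitor or hold. In row 4 it does not fit.

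**3. Does the note exempt row 4?** It speaks of any one criterion in the list above and names no rows. The first note uses retesting for the criteria that lead to individual discontinuation. The third note's reference to a criterion confirmed by retesting is most naturally those same criteria. The Gilbert case has its own note, so the general permission is not needed to cover it.

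**4. What limits the harm**

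- Section 7.1.1 asks for every attempt at repeat chemistries within 24 hours.
- No dose may be given before the retest is evaluated. Planned dosing days 1, 4, 8, 11, 15 and 22 give gaps of 3, 4, 3, 4 and 7 days, then weekly. The shortest planned gap is 3 × 24 = 72 hours against a 24-hour repeat. Visit windows can shorten that gap, but the bar on dosing before the retest is evaluated does not depend on it.
- The Medical Monitor is to be told within 24 hours of any Table 6 liver event, in order to confirm that treatment has ceased.

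**5. Appendix 6.** Its procedure list contains no repeat of ALT, bilirubin or INR. It takes its criteria from Section 7.1.1, however, and both that section and Section 7.1 put confirmation before withdrawal. The duration rules in rows 1 and 2 cannot be triggered by a single value: twice weekly for 4 weeks is at least 2 × 4 = 8 values.

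**The case against.** The strongest defence is that the note was written for a wider class of events. It directly follows a note on clinically significant deterioration in liver parameters, a broader category than the discontinuation conditions. Section 7.1.1 also leaves room for investigator judgement when no stopping rule is met. On that reading the permission is reasonable for the monitor and hold rows, and it accommodates Gilbert syndrome. This stands as a plausible account of intent. It does not settle the wording, because nothing in the note excludes row 4.

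A reader might infer that a site may keep dosing at its own discretion after confirmed severe liver injury. The documents do not support that. The note itself requires Medical Monitor discussion, a separate procedure requires notification within 24 hours to confirm cessation, and the site would have to override both mandatory statements and the row 4 instruction.

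A reader might also infer that Appendix 6 ends treatment irreversibly on one unconfirmed value, since Section 7.1.5 bars rechallenge and narrowly limits restart. That is not supported either. The appendix applies criteria defined in Section 7.1.1, where confirmation is already required, and an appendix need not repeat a rule from the section it cites. What remains is that its first step, read alone, omits the confirmation and could be clearer.

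**Conclusion.** Section 7.1.1 contradicts itself on a liver safety stopping rule and should be corrected. The practical scope is small. The conflict matters mainly for the last row of Table 6 at first occurrence, Medical Monitor contact is already required, and dosing is barred until the retest has been evaluated. The Appendix 6 wording is a minor alignment point and not a second contradiction.

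The conclusion rests on the note being read as written, without an unstated restriction to the monitor and hold rows. The documents do not say how often row 4 events would occur, so no frequency is claimed.

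A reader might look for a consequence for the efficacy result. None is shown: the primary estimand ignores discontinuation of study treatment under a treatment policy strategy, apart from wide disruptive events (protocol Section 9.4.2.1, SAP Section 4.2.2.2). The point concerns safety conduct and consistency between sites.

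**What to change.** Replace the third Table 6 note with: *If a condition in the Discontinuation column is met and its laboratory values are confirmed by retesting, study treatment must be permanently discontinued, in discussion with the Medical Monitor; for other rows follow the monitor or hold instructions.* Keep the sentence barring a dose before the retest is evaluated. Keep the Gilbert syndrome note as the only exception to stopping. The restart route in Section 7.1.5 applies after stopping and is unaffected.

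As a minor alignment, replace the first step in Appendix 6 with: *Hold study treatment immediately; permanently discontinue once laboratory criteria are confirmed by retest per Section 7.1.1 (no laboratory retest of the hepatitis-symptom component is needed; the accompanying ALT value is still retested).* The bracket is needed because a blood sample cannot confirm a symptom.

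The cost is two wording changes in the protocol, with no new visits or tests and no SAP change.

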7.1.2. Drug Induced Vascular Injury and Complement Stopping Criteria

If any of the following are observed, results should be confirmed with a repeat sample collection and analysis, and if confirmed, further evaluation for alternative causes should be pursued in consultation with the Medical Monitor.

Repeat sample collection of C3, C4, Bb, C5a would be triggered by changes in the clinical signs and symptoms of complement activation (≥2+ haematuria; increasing urine ACR; vasculitic or purpuric rash; peripheral neuropathy; jaundice). Additional complement analyses for example CH50, Factor B level, Factor H level, sC5b-9 should also be considered in discussion with the Medical Monitor and Safety Panels.

1. Persisting & deteriorating longitudinal trends in change from baseline for C3 and/or C4 defined as:

- a. If participant's baseline C3 and/or C4 is *within* the lab's normal range at baseline: there is a sequential decline in C3 and/or C4 once levels have fallen below LLN for ≥4 weeks OR
- b. If participant's baseline C3 and/or C4 is *below* the lab's LLN at baseline: there is further sequential decline in C3 and/or C4 for ≥4 weeks OR
- c. Regardless of baseline C3 and/or C4 level: there is a ≥80% reduction in the participant's C3 and/or C4 level at any point

AND

- d. There is an associated ≥3-fold increase in Bb and/or C5a from participant's baseline OR
- e. There are associated biochemical sequelae for example, a rising high sensitivity C-reactive protein (hs-CRP); rising monocyte chemoattractant protein-1 (MCP-1); new thrombocytopenia, new renal impairment with no other explanation such as intercurrent infection OR
- f. There are associated clinical sequelae, for example, ≥2+ haematuria; increasing urine ACR; vasculitic or purpuric rash; peripheral neuropathy; jaundice OR
- g. There is new cANCA or pANCA positivity

2. Persisting & deteriorating longitudinal trends in change from baseline for Bb and/or C5a where

- a. There is a \geq 3-fold increase in Bb and/or C5a over baseline AND
- b. This is persisting or increasing week on week in sequential data plots OR
- c. There are associated biochemical sequelae for example, a rising hsCRP; rising MCP-1, new thrombocytopenia, new renal impairment with no other explanation such as intercurrent infection OR
- d. There are associated clinical sequelae, for example, ≥2+ haematuria; increasing urine ACR, vasculitic or purpuric rash; peripheral neuropathy; jaundice or any combination of these OR
- e. There is new cANCA or pANCA positivity

Treatment Hold/Treatment Discontinuation

- Hold study treatment during evaluation of alternative causes for decreased C3 and/or C4 associated with increased inflammatory markers including one or more of hs-CRP, MCP-1, Bb and C5a
- Discontinue study treatment permanently if persistent change from baseline (≥4 weeks) in biomarker pattern (decreased C3/C4 associated with increased inflammatory markers including one or more of hsCRP, MCP-1, Bb, C5a) without clear alternative explanation.
- Discontinue study treatment permanently if suspect clinical sequelae of complement activation, drug induced vascular injury, vasculitis or auto-immunity regardless of biomarkers changes or persistence.

7.1.3. Haematological Stopping Criteria

If a participant develops signs or symptoms of thrombocytopenia, obtain a platelet count (local lab) as soon as possible and hold dosing until the platelet count is confirmed.

If the platelet count is uninterpretable or a decreasing trend is noted below LLN reference range, re-check the platelet counts as soon as possible (the investigator may, at their discretion, opt to have the participant come to their next scheduled visit OR ask the participant to come earlier than their scheduled visit, as they feel appropriate based on review of the participant's clinical presentation and laboratory results). Samples showing platelet clumping should also be repeated.

Participants with platelet values below 75×10^9 /L will undergo further assessment including, but not necessarily limited to, anti-platelet antibodies. If the participant has a positive anti-platelet antibody, study treatment should be discontinued permanently. Monitor until platelet abnormalities resolve, stabilize, or return to within baseline values.

Table 7 Haematological Stopping Criteria

Platelet Count	Monitoring	Treatment
75 X 10 ⁹ /L ≤ Platelets <100 X 10 ⁹ /L	Monitor weekly, results of local platelet count must be available prior to dosing	Hold treatment until platelets return to ≥100 x10 ⁹ /L
50 X 10 ⁹ /L ≤ Platelets1 <75 X 10 ⁹ /L	Monitor every 2-3 days until three successive measurements ≥75 x10 ⁹ /L, then weekly Assess anti-platelet antibodies	[if positive for anti-platelet antibodies, study treatment should be discontinued immediately]
<50 x 10 ⁹ /L	Monitor daily until ≥25 x10 ⁹ /L, monitor every 2-3 days until three successive measurements ≥75 x10 ⁹ /L, then weekly until platelets ≥100 x10 ⁹ /L Assess anti-platelet antibodies	Discontinue treatment permanently Glucocorticoids recommended (unless the participant has a medical contraindication to receiving glucocorticoids), and discontinuation of any antiplatelet medicinal products/NSAIDs/anticoagulants

7.1.4. Drug Induced Kidney Injury (Renal) Stopping Criteria

If any of the following are observed, results should be confirmed, and if confirmed, further evaluation for alternative causes should be pursued in consultation with the Medical Monitor:

- Persistent ACR ≥ 0.03 mg/mg (≥ 30 mg/g)
- Blood in urinalysis ≥5 RBC per high power field (HPF) confirmed by urine microscopy

• Persistent elevation of serum creatinine (>26.52 μmol/L or 0.3 mg/dL change from baseline)

Following confirmation of the criteria above, further evaluation may include but not be limited to a 24-hour urine analysis, consultation with a nephrology specialist, renal ultrasound, urine microscopy, serum urea and creatinine, platelet count, urgent serum vasculitis screen [including ANCA, ANA, dsDNA, cryoglobulins], serum protein electrophoresis (SPEP)/urine protein electrophoresis (UPEP), and complement panel (C3, C4, C5a and Bb). Further evaluation and actions should be determined by the investigator in consultation with the Medical Monitor.

Treatment Hold/Treatment Discontinuation

- Hold study treatment in participants who develop ACR ≥0.5 mg/mg (500 mg/g), or eGFR >25% reduction from pre-dose range, pending consultation with the Medical Monitor and further evaluation of the cause.
 - If a dose is held, once eGFR increases to within baseline, ACR decreases to <0.5 mg/mg (500 mg/g), or the underlying cause of the decline in renal function is corrected, weekly dosing may be reinitiated after consultation with the Medical Monitor
 - o Participants must be monitored weekly until ACR or eGFR resolve, stabilize, or return to within pre-dose range
- Hold study treatment in participants with ACR ≥2 mg/mg (2000 mg/g), perform further evaluation for acute glomerulonephritis, as clinically indicated. If acute glomerulonephritis is confirmed or probable (i.e., meets clinical definition of rapidly progressive glomerulonephritis [RPGN] if biopsy not feasible), GSK3228836 should be permanently discontinued
 - o Participants must be monitored weekly until ACR resolves, stabilizes, or returns to within baseline values
- Delay in treatment of suspected RPGN should be avoided.

